3.2 Trial Setting

[figure not shown]
The trial will be performed in a tertiary care setting involving all five of the designated adult lung transplant centres in the UK. This will allow all adult UK bilateral lung transplant patients who develop CLAD to learn about the trial and decide if they wish to participate.

3.3 Flow Charts of Study Design and Research Activity

3.3.1 Overview of Study Design

3.3.2 Flow Chart of Research Activity

3.4 Primary and secondary outcome measures/endpoints

3.4.1 Primary outcome measure

Lung function stabilisation will be derived from change in FEV1 and FVC at 12 and 24 weeks compared to baseline at study entry. At baseline and 24 weeks FEV1 and FVC will be taken from Full Pulmonary Function Tests (PFT) carried out as a research assessment. At 12 weeks FEV1 and FVC values will be taken from those collected as part of routine clinical assessment.

Full Pulmonary Function Tests

Full pulmonary function tests to include FEV1, FVC, FEF25-75, Flow-volume loop, TLC, RV, Va, TLCO and KCO should be performed in a fully accredited lung function laboratory by or under the close supervision of a qualified pulmonary physiologist. Results should be provided as absolute values, % predicted values and z-scores. All spirometry should be performed according to ATS/ERS standards. If a bronchodilator response is performed, then post-bronchodilator FEV1 and FVC values should be reported.

Routine spirometry tests

Routine clinic spirometry as collected regularly in the transplant clinic should be performed in accordance with usual clinical practice in the transplant centre by a trained individual able to ensure adequate reproducibility/quality control of the test and reporting of absolute values of FEV1 and FVC. Tests can be performed in either an accredited lung function laboratory or using a desktop or handheld spirometer as long as adequately supervised. Interpretation of the routine spirometry will be by the participant's lung transplant physician. Home spirometry results performed by participants using a handheld spirometer already in their possession can be used in place of routine clinic spirometry if it is not possible for the participant to attend. In such cases the principal investigator must be confident the participant is trained in its use and able to perform reproducible spirometry. Home spirometry cannot be used to replace the baseline and end of study full pulmonary function tests or the 12-week assessment time point.

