7.3 Lung Function

Lung function stabilisation – defined as a less than or equal to a 10% loss in FEV1 and FVC from study baseline to 24 weeks.

Rapid decline – defined as a greater than 20% fall in FEV1 or FVC in the first 12 weeks from study baseline.

Non-responders – As outlined in the study flow chart in Section 3.3, a non-responder is defined as someone who experiences a decline in FEV1 or FVC of more than 10% at 24 weeks compared to baseline readings due to progressive CLAD. A non-responder may also be someone with a decline in FEV1 or FVC of >20% within 12 weeks of the baseline visit that is confirmed as being due to progressive CLAD.

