- Supplementary Oxygen as needed
- Bronchodilators as needed
- Psychological Support as needed
- Pulmonary rehab as indicated
- Do not use Leukotriene Receptor Antagonists
- Do not use inhaled corticosteroids
- Do not use Total Lymphoid Irradiation

Standard care of lung transplant recipients with definite CLAD (after completion or withdrawal from study)

- Consider any of the following as potential rescue therapies
 - Total Lymphoid Irradiation
 - Extracorporeal Photopheresis if not received within E-CLAD UK trial
 - Other therapies at the discretion of the physician providing usual care
 - Other investigational agents if applicable

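### The full-PFT rule lets an optional bronchodilator test decide which FEV1 and FVC are reported, without requiring the same state at baseline and week 24

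*Protocol*

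**What the plan says.** Section 3.4.1 gives two sources for the primary endpoint.

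- Baseline and week 24: "At baseline and 24 weeks FEV1 and FVC will be taken from Full Pulmonary Function Tests (PFT) carried out as a research assessment".
- Week 12: "At 12 weeks FEV1 and FVC values will be taken from those collected as part of routine clinical assessment".

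The bronchodilator sentence, "If a bronchodilator response is performed, then post-bronchodilator FEV1 and FVC values should be reported", stands under the full-PFT heading. Reversibility testing is not in the list of required measurements there, nor in the baseline list (5.2.4) or the final-assessment list (5.6). Nothing says when it is done, or that doing it at one visit means doing it at the other.

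Routine spirometry "should be performed in accordance with usual clinical practice in the transplant centre", and no bronchodilator state is given for it. The general standard, "All spirometry should be performed according to ATS/ERS standards", does not state one in the protocol either. Standard of care within the study (Appendix 1) allows "Bronchodilators as needed", with no timing relative to spirometry.

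Section 7.3 sets the lines. Stabilisation is "defined as a less than or equal to a 10% loss in FEV1 and FVC from study baseline to 24 weeks". Rapid decline is "defined as a greater than 20% fall in FEV1 or FVC in the first 12 weeks from study baseline".

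**The concern.** The week-24 component of the primary endpoint is a within-person percentage change judged against a fixed cut-off. It is interpretable only if both values are measured under the same conditions. Here the reported condition depends on whether an optional test happened to be done at that visit.

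A difference in state at one visit is then read as loss or preservation of lung function. It can change a participant's responder status. Because section 10.3.1 models the continuous changes in FEV1 and FVC, it also shifts the modelled value of every mismatched participant, including those far from the line. If mismatch were more common in one arm, the treatment comparison would be biased. If not, it adds noise.

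**Working it through.** **Inputs from the protocol.** 90 participants, so 45 per arm; one-sided 5% error; response rates 30% (SOC) and 55% (ECP); stated power 80% (section 10.1); cut-offs of 10% at week 24 and 20% at week 12 (section 7.3).

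**Assumed inputs, not in the protocol.** Proportional bronchodilator gain g, the same at both visits, 3% to 12%. SD of the 24-week relative change in FEV1, 10 to 20 percentage points, normally distributed. Only FEV1 is modelled.

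**The plan's own figure.** For 30% versus 55% at 45 per arm, the unpooled normal approximation gives 79.8% power and the pooled one 78.2%. Both are within 2 points of the stated 80%. The pooled 78.2% is the reference below.

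**How the 10% line moves.** Let r be the true ratio of week-24 to baseline function.

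- Post-bronchodilator baseline, pre-bronchodilator week 24: the measured ratio is r/(1+g). Passing needs r ≥ 0.90(1+g). With g = 5%, 0.90 × 1.05 = 0.945, a true loss of 5.5%.
- Pre-bronchodilator baseline, post-bronchodilator week 24: the measured ratio is r(1+g). Passing needs r ≥ 0.90/(1+g). With g = 5%, 0.90/1.05 = 0.857, a true loss of 14.3%.

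| g | Apparent loss with no true change (post, then pre) | Effective line, post then pre | Effective line, pre then post |
|---|---|---|---|
| 3% | 2.9% | 7.3% | 12.6% |
| 5% | 4.8% | 5.5% | 14.3% |
| 8% | 7.4% | 2.8% | 16.7% |
| 10% | 9.1% | 1.0% | 18.2% |
| 12% | 10.7% | below zero | 19.6% |

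With no true change, the apparent loss g/(1+g) exceeds 10% only when g is above 0.10/0.90 = 11.1%. At the 20% week-12 line the same calculation needs g above 0.20/0.80 = 25%.

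**Effect on a mismatched participant's chance of passing** (g = 5%; mean set so that the true pass rate is 30% or 55%).

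| SD | True 30%: post then pre / pre then post | True 55%: post then pre / pre then post |
|---|---|---|
| 10 | 16.5% / 46.2% | 37.3% / 71.0% |
| 15 | 20.5% / 40.6% | 43.1% / 66.0% |
| 20 | 22.7% / 37.8% | 46.0% / 63.3% |

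**Mismatch balanced between arms.** Suppose 20% of participants in each arm are mismatched, half in each direction, with SD 15. At g = 5% the rates become 30.1% and 54.9%, and power goes from 78.2% to 77.6%. At g = 10% they become 30.4% and 54.7%, with power 76.0%. Over SD 10 to 20 and g of 5% or 10%, power lies between 73.6% and 77.9%.

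**Mismatch in one arm only (extreme case).** Take no true effect, 30% in both arms, SD 15, and a simple additive shift of 5 points.

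- The mean change is −10 − 0.524 × 15 = −17.87. After the shift, the chance of passing is P(Z ≥ (−15 + 17.87)/15) = P(Z ≥ 0.191) = 42.4%, a rise of 12.4 points. From 55% the rise is 12.7 points. The proportional model above gives 10.6 and 11.0.
- If 20% of ECP week-24 tests and no SOC tests are mismatched in this direction, the arm difference shifts by 0.20 × 12.4 = 2.5 points.
- The standard error is √(2 × 0.3 × 0.7/45) = 0.0966, and 0.025/0.0966 = 0.26. The one-sided error becomes P(Z > 1.645 − 0.26) = 8.3%.
- By the same formula, a one-arm excess of 10% of participants gives about 6.5%, and 5% gives about 5.7%.

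**The case against.** The strongest reply is that this is a small matter of measurement standardisation. The test is optional and on no required list. Mismatch needs it at exactly one of two visits, and balanced mismatch barely moves power. The sentence says that post-bronchodilator values should be reported, not that the pre-bronchodilator value is discarded, so the analysis plan could name the value used. The calculations rest on an assumed gain and SD. They place composite response rates on FEV1 alone although FVC must also pass, and they use a two-proportion test rather than the planned model.

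Most of this stands as a limit on size. It does not close the gap. If only the post-bronchodilator value is reported and the state is not recorded, no later analysis can restore a like-for-like comparison. If both are reported, this document still does not say which one enters the endpoint.

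A reader might infer four stronger things that the protocol does not support.

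- That the rule governs week 12. It sits under full PFTs; week 12 comes from routine spirometry and is judged against 20%. The gap there is that no state is set.
- That mismatch alone carries a stable participant below the 10% line. That needs a post-bronchodilator baseline and a gain above 11.1%; smaller gains reclassify only participants whose true change is already near the line.
- That unblinded staff choose when to test. Section 5.3.3 says participants, clinicians and the trials unit know the allocation, but no section says who orders a response test or whether laboratory staff know the arm.
- That the type I error is inflated to 8%. That is a constructed extreme, and nothing in the protocol shows differential testing.

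**Conclusion.** The concern holds for baseline against week 24. As written, section 3.4.1 permits unlike values to be compared in the primary endpoint and does not resolve the mismatch. The consequence is misclassification near the 10% line and added error in the modelled changes. The power loss is small if mismatch is balanced: under 5 points in every case examined with 20% of participants mismatched. Bias depends on testing that differs by arm, which the open-label design allows but which is not shown. All sizes rest on the assumed gain, SD and mismatch rate, and the FVC requirement would reduce the FEV1-only effects by an amount not calculated here. The correction is worth making because it is nearly free and the information cannot be recovered afterwards if it is not recorded.

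**What to change.** Replace the sentence in section 3.4.1 with a requirement along these lines:

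- For each participant, baseline and week-24 endpoint FEV1 and FVC are compared in the same bronchodilator state.
- Where a response test is done, both pre- and post-bronchodilator values are recorded. The endpoint uses the state available at both visits, which is pre-bronchodilator when only one visit had the test. If both visits had it, the text should name in advance which state is used.
- The state is recorded in the eCRF at each endpoint visit, including week 12, and the matching state is used at week 12 where it is available. Because week 12 follows each centre's own practice, a match may not always exist; recording the state at least makes this visible.

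The cost is a short change to 3.4.1 and, if not already present, an eCRF field. No test is added, because a response test already yields a pre-bronchodilator value. With matching states and a stable gain the shift is zero. The planned sample size is unaffected, since it rests on assumed response rates.

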3.4.2 Secondary outcome measures

Spirometry Tests

FEV1 and FVC values collected as part of routine clinic spirometry and research pulmonary function tests along with historical clinical spirometry data from medical records will be used to calculate rate of decline and absolute change in lung allograft dysfunction. Calculation of rate of change will require at least 3 measurements from the period leading up to randomisation (maximum 26 weeks but ideally within 12 weeks) and the 24 weeks after randomisation. Recordings should be performed as detailed in section 3.4.1.

6 Minute Walk Test (6MWT)

Change in exercise capacity will be measured from baseline to 24 weeks using the change in the 6MWT distance. The 6MWT is a self-paced 6-minute walk recording the distance walked in metres (19). The walking track will be standardised for each site with all participants receiving standardised instructions and encouragement. An oximeter will be attached to the participant during the walk for continuous monitoring of oxygen saturations and heart rate. The 6MWT test will be performed and recorded once for the baseline and final assessments. If there are technical issues which affect the quality of the test or reliability of the result, then it will be repeated after a period of 30 minutes between the two walks to allow the oxygen saturation and heart rate to return to resting levels.

The following measurements will be collected during the 6MWT:

Total Distance Walked during the 6 minutes in metres

Resting oxygen saturation (%) at start, lowest saturation during the test and saturation at end

Number of stops and amount of time spent stopped

Degree of breathlessness using the Borg Score (0-10)

EQ-5D-5L

The EQ-5D-5L will be collected at baseline and 24 weeks to assess change in participant reported quality of life.

The EQ-5D-5L general health questionnaire evaluates five domains (-5D), which include: mobility, self-care, usual activities, pain/discomfort, and anxiety/depression (20). This is a two-page questionnaire that consists of five dimensions, with the responses recorded at five levels (5L) of severity (no problems; some problems or extreme problems). The second page consists of a standard vertical 20cm visual analogue scale (EQ-5D VAS) which is transformed to a scale of 0 to 100 measuring current health-related quality of life. Each participant's health state, derived from the EQ-5D, will be measured before and after the intervention period determine the change in their health gain or loss.

SF-36 V2

The SF-36 V2 will be collected at baseline and 24 weeks to assess change in participant reported health status.

The SF-36 medical outcomes study questionnaire short form health survey involves 36 questions grouped to eight scales of health including: vitality, physical functioning, bodily pain, general health perceptions, physical role functioning, social role functioning, and mental health (21). Responses are recorded either on 5-point scales, 3-point scales or as dichotomous (yes/no) items. Sections are then scored on the weighted sums of the questions in each section in a scale of 0 to 100. These are combined to produce two psychometrically based physical and mental health summary measures.

Case Report Form (CRF)

CRFs will be used at each assessment time point to capture change in CLAD symptoms, changes to medications and routine clinical care and new interventions. Changes to CLAD stage will be captured as well as results of routine bloods, Chest X-rays, PFT's and other relevant assessments. All aspects of standard of care received will be collected for all participants.

ECP CRF's will capture all relevant details associated with ECP treatment including compliance and deviations from the planned intervention.

CRF's will be used to capture any deviation and adverse events in all participants.

The majority of CRFs will be electronic and completed via the online trial database. For those sites where the ECP unit sits separately to the transplant research team, a paper CRF will be provided for completion. Once completed this paper CRF must be provided to the relevant research team for data entry into the eCRF. The paper CRF must be kept, with the original filed in the Investigator Site File and a copy filed/uploaded to the participants medical notes at the research site.

4. TRIAL PARTICIPANTS

Patients aged 16 and over who have received a bilateral (a.k.a. single sequential) lung or heart and (bilateral) lung transplantation that fulfil the ISHLT 2019 diagnostic criteria for CLAD.

Eligibility must be assessed by a medically qualified doctor and this assessment documented in the participant's medical notes. Only personnel formally delegated by the Principal Investigator (PI) to assess eligibility may perform this task.

Patients are eligible for the trial if **all** the following inclusion and exclusion criteria apply.

4.1 Inclusion Criteria

- Adults (≥ 16 years of age) with body weight ≥ 30 kg.
- Bilateral lung or heart and (bilateral) lung transplant recipients.
- Confirmed diagnosis of CLAD stages 1, 2 or 3 as per ISHLT 2019 consensus definition (see section 7 for definition).
- New CLAD diagnosis or prior diagnosis with evidence of current progressive disease.
- Exclusion of non-CLAD causes for decline in lung function by high-resolution computed tomography (HRCT) thorax and bronchoscopy +/- transbronchial biopsy within 12 weeks of first CLAD diagnoses.
- Adequate treatment of potential non-CLAD causes of a decline in lung function (e.g. acute cellular or acute humoral rejection, infections, airway anastomotic strictures and medical treatment for gastroesophageal reflux).
- Progressive decline in FEV1 ($\geq 10\%$) while on azithromycin for ≥ 6 weeks.
- Capacity to provide written informed consent.
- A minimum of 2 recorded FEV1 and FVC measurements (including home spirometry) obtained during the 26 weeks preceding consent*. Measurements must be at least 3 weeks apart with the last measurement at least 3 weeks prior to consent

* FEV1 and FVC values collected as part of routine clinic spirometry and research pulmonary function tests along with historical clinical spirometry data from medical records will be used. Ideally readings should be from the preceding 12 weeks but up to 26 weeks prior to consent is acceptable. These will ideally have been collected at clinical appointments, but home spirometry readings are also acceptable.

4.2 Exclusion Criteria

- Single lung transplant recipients.
- Female patients who are breastfeeding, pregnant or planning to become pregnant during the timeframe of study participation.
- Current treatment with or past history of TLI completed within the last 12 months.
- ≤ 1 -month wash-out from any other investigational therapies for CLAD.
- Inability to perform lung function tests or adhere to study protocol as judged by supervising clinician.
- History of Hematopoietic Stem Cell Transplantation (HSCT).
- Patients who are on a retransplant waiting list.
- Current participation in another interventional clinical trial, or participation in a clinical trial of an investigational agent in the previous 4 weeks from consent.

- Patients with inadequate vascular access (peripheral or central) options to perform ECP.
- Any contraindication to receiving ECP. These include:
 - Previous allergic reaction to methoxsalen, another psoralen compound, or any of the other UVADEX® ingredients.
 - Co-existing untreated skin cancer* (melanoma, basal cell or squamous cell cancer).
 - Any disease which involves sensitivity to light such as porphyria, systemic lupus erythematosus or albinism
 - Previous removal of spleen
 - Blood clotting disorder or an increased white blood cell count $>25 \times 10^9$ per litre.
 - Significant heart disease or severe anaemia causing inability to tolerate blood volume shifts associated with ECP.
 - Aphakia or lens removed from either eye (unless already blind in eye without a lens).
 - Sexually active men and women of childbearing potential unless adequate contraception is used during treatment.

*Patients with co-existing treated skin cancer should be assessed and counselled on the balance of risks of harm from their skin cancer after exposure to methoxsalen or from their CLAD diagnosis in determining if this constitutes an exclusion criterion.

NB: Enrolling a patient onto the trial who does not meet the inclusion/exclusion criteria is considered a protocol waiver and is in breach of Regulation 29 (SI 2004/1031) of the Medicines for Human Use (Clinical Trials) Regulations 2004. PROTOCOL WAIVERS ARE NOT PERMITTED.

4.3 Effective Methods of Contraception

To be eligible for the trial, female patients of child-bearing potential who are sexually active must confirm that they understand the need to use a highly effective method of contraception from 1 month prior to enrolling in the trial until the end of their trial participation. Female patients of child-bearing potential must also confirm they understand that their male partner should use an effective method of contraception for the duration of any ECP treatment. Highly effective methods include:

Female participants	Male partners of female participants

 • Combined (estrogen and progesterone containing) hormonal contraception associated with inhibition of ovulation (oral, intravaginal, transdermal) • progesterone-only hormonal contraceptive associated with inhibition of ovulation (oral, injectable, implantable) • intrauterine device (IUD) • intrauterine hormone-releasing system (IUS) • bilateral tube occlusion or hysterectomy • vasectomised partner (>3 months earlier) • sexual abstinence 	
 • Condom • Sexual abstinence • Vasectomy

Fertile male patients with female partners of child-bearing potential must confirm they understand the need to use a barrier method of contraception from randomisation into the trial up until the end of any ECP treatment. They must also confirm they understand that their female partner should use

an effective method of contraception from the time of first ECP treatment until end of their trial participation as detailed below:

Male participants	Female partners of male participants

 • Condom • Sexual abstinence • Vasectomy 	
 • Combined (estrogen and progesterone containing) hormonal contraception associated with inhibition of ovulation (oral, intravaginal, transdermal) • progesterone-only hormonal contraceptive associated with inhibition of ovulation (oral, injectable, implantable) • intrauterine device (IUD) • intrauterine hormone-releasing system (IUS) • bilateral tube occlusion or hysterectomy • vasectomised partner (>3 months earlier) • sexual abstinence

Details about applicable contraceptive methods explained to participants should be recorded in the participant's medical record. For both male and female patients, the practice of sexual abstinence must be in line with preferred and usual lifestyle and documented in the participant's medical record and eCRF. Periodic abstinence (e.g., calendar, ovulation, symptothermal, post-ovulation methods) and withdrawal are not considered acceptable methods of highly effective contraception for the purposes of the trial.

Females who are amenorrhic for more than 12 months are considered not to be of child-bearing potential.

